2.4.3 Rationale for Booster Doses of Vaccine

Decreased immune responses in patients with malignancies create a need to identify improved vaccination strategies for this vulnerable population. One approach involves repeat ‘booster’ vaccinations. Previous studies investigating booster vaccinations with the influenza vaccine have produced disappointing results in CLL and after allogeneic stem cell transplant[21, 22]. However, booster vaccinations appear to be effective in certain immunocompromised populations, including after solid organ transplant or in plasma cell dyscrasias [23, 24]. Importantly, it is unknown whether booster vaccinations with novel adjuvanted vaccines will be able to increase immunogenicity in patients with hematologic malignancies, particularly in patients receiving cancer directed oral targeted therapy or CAR T cell therapy. In order to determine whether booster vaccinations can improve seroconversion rates, booster vaccinations will be offered to subjects who have completed a standard vaccine series. For the purpose of this study, patients will receive booster doses of mRNA-1273 regardless of their serologic status.

All patients who receive booster vaccinations may benefit from enhanced and prolonged immunogenicity, which will be measured for all cohorts enrolled.

2.4.4 Rationale for Booster Doses for Patients on CAR T Cell Therapies for B Cell Malignancies

The development of CARTx for B cell malignancies is a major milestone in cancer treatment. However, CARTx recipients are at high risk for infectious complications due to prior anti-tumor treatments and the immune-related adverse event (irAE) of prolonged B cell depletion from on-target/off-tumor side effects.

The goals of the currently funded U01 grant within the Cancer Moonshot PI-DDN (U01 CA247548-01) are to define the humoral irAEs related to B cell depletion by studying the effects of CD19- and BCMA-targeted CARTx on pre-existing and de novo pathogen-specific immunity. We will determine the proportion of adults with seroprotection to vaccine-preventable and other infections, and how these findings change over time, in a prospective cohort study. In addition, we will perform an observational study of patients who are receiving routine vaccinations after CARTx to define the frequency and correlates of vaccine responses.

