11.4.1.2 Per-Protocol Set

The Per-Protocol (PP) Set consists of all FAS participants who meet all of the following criteria:

- Complied with the injection schedule.

- Complied with the timings of immunogenicity blood sampling to have post-injection results available for at least one assay component corresponding to the immunogenicity analysis objective.
- Have had no major protocol deviations that impact immune response during the period corresponding to the immunogenicity analysis objective.

The PP Set will serve as the primary set for the analysis of immunogenicity data in this study.

11.4.1.3 **Solicited Safety Set**

The Solicited Safety Set consists of all participants who received at least one study injection, and contribute any solicited AR data; i.e., have at least one post-baseline solicited safety assessment. The Solicited Safety Set will be used for the analyses of solicited ARs.

11.4.1.4 **Safety Set**

The Safety Set consists of all participants who received at least one study injection. The Safety Set will be used for analysis of safety except for the solicited ARs.

11.4.2 **Statistical Analyses**

11.4.2.1 **Immunogenicity Analyses**

The analyses of immunogenicity will be based on the PP Set. If the number of participants in the FAS and PP Set differ (defined as the difference divided by the total number of participants in the PP Set) by more than 10%, supportive analyses of immunogenicity may be conducted using the FAS.

For the primary immunogenicity endpoint, geometric mean titer (GMT) of specific bAb with corresponding 95% CI at each timepoint and geometric mean fold rise (GMFR) of specific bAb with corresponding 95% CI at each post-baseline timepoint over pre-injection baseline at Day 1 will be provided. Descriptive summary statistics including median, minimum, and maximum will also be provided.

For the secondary immunogenicity endpoint, GMT of specific nAb with corresponding 95% CI at each timepoint and GMFR of specific nAb with corresponding 95% CI at each post-baseline timepoint over pre-injection baseline at Day 1 will be provided. Descriptive summary statistics including median, minimum, and maximum will also be provided. For summarizations of GMT values, antibody values reported as below the LLOQ will be replaced by $0.5 \times \text{LLOQ}$. Values that are greater than the upper limit of quantification (ULOQ) will be converted to the ULOQ.

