The number and percentage of participants with $\text{GMFR} \geq 2$, $\text{GMFR} \geq 3$, and $\text{GMFR} \geq 4$ of serum SARS-CoV-2-specific nAb titers and participants with seroconversion due to vaccination from baseline will be provided with 2-sided 95% CI using the Clopper-Pearson method at each post-baseline timepoint. Seroconversion at a participant level is defined as:

- For subjects with no detectable antibody titer ($< \text{LOD}$) at baseline: post-vaccination titer $\geq \text{LLOQ}$
- For subjects with a positive baseline titer ($> \text{LOD}$): post-vaccination titer ≥ 4 times the LLOQ

- For subjects with a baseline titer \geq LLOQ: post-vaccination titer \geq a 4-fold rise compared with baseline titer

GMT with corresponding 95% CI will be provided (for each group) at each time point. The 95% CI will be calculated based on the t-distribution of the log-transformed values and transformed back to the original scale for presentation.

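### Capping titers at the ULOQ means that, if the cap is applied to fold rises, a participant with baseline above ULOQ/4 cannot show a 4-fold rise; the booster cohorts are most exposed, and the size is unknown

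*Combined protocol and SAP*

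**What the plan says.** Section 11.4.2.1 (Immunogenicity Analyses) reports GMT and GMFR for bAb (primary) and nAb (secondary), with fold rise taken "over pre-injection baseline at Day 1". At the end of the nAb paragraph come two substitution rules. The lower one has a stated scope: "For summarizations of GMT values, antibody values reported as below the LLOQ will be replaced by" half the LLOQ. The upper one follows at once with no scope of its own: "Values that are greater than the upper limit of quantification (ULOQ) will be converted to the ULOQ".

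The same section then reports the number and percentage of participants with rises of at least 2, 3 and 4 "of serum SARS-CoV-2-specific nAb titers and participants with seroconversion due to vaccination from baseline", each with a "2-sided 95% CI using the Clopper-Pearson method at each post-baseline timepoint". Seroconversion has three criteria:

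- baseline below LOD: post-vaccination titer at least LLOQ;
- "For subjects with a positive baseline titer" (above LOD): post-vaccination titer at least 4 times LLOQ;
- baseline at or above LLOQ: at least "a 4-fold rise compared with baseline titer".

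On who is boosted, section 2.4.3 states that "patients will receive booster doses of mRNA-1273 regardless of their serologic status". Section 5.2.3 requires a completed initial series and admits people already boosted off study. Sections 3.1 and 6.1.3 and Appendix G allow second and third boosters from 4 weeks after the previous dose, and each resets Day 1. Section 11.1 says that there is no hypothesis testing and that the aim is estimation.

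**The concern.** A fold rise is a ratio of two measured values. If both are capped at the ULOQ, a participant who starts close to the ULOQ has no room to show a rise, whatever the vaccine did. That participant still sits in the denominator of the fold-rise percentages and still contributes a compressed ratio to the GMFR.

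High baselines are plausible in the booster cohorts, where people arrive already vaccinated and a second or third booster may have a baseline taken only weeks after the previous dose. Estimates are the only product of this trial, and section 2.4.3 asks whether boosters can improve seroconversion. A ceiling would pull the reported booster effect down, most where pre-existing immunity is best, and the Clopper-Pearson and t-based intervals would not reflect it.

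**Working it through.** The plan gives no figure to reproduce here. It states no ULOQ, LLOQ, assay range, baseline distribution or expected rise.

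**1. The ceiling (no assumptions beyond the cap).** Largest observable rise = ULOQ / min(baseline, ULOQ).

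| Baseline / ULOQ | Largest observable rise | ≥4 possible | ≥3 possible | ≥2 possible |
|---|---|---|---|---|
| 0.25 | 4.00 | yes | yes | yes |
| 0.30 | 3.33 | no | yes | yes |
| 0.40 | 2.50 | no | no | yes |
| 0.60 | 1.67 | no | no | no |
| 1 or more | 1.00 | no | no | no |

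**2. Seroconversion.** Under the third criterion, a baseline above ULOQ/4 can never qualify. The second criterion has no upper bound on baseline, so it covers the same person. If ULOQ/LLOQ is at least 16, then ULOQ/4 ≥ 4 × LLOQ, and a baseline above ULOQ/4 already meets the second criterion with no rise at all. The plan does not say which criterion prevails.

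**3. Limit on a cohort's rate.** If k of n participants start above ULOQ/4, the highest attainable 4-fold rate is (n − k)/n. With assumed k and exact 95% limits:

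- n = 20: k = 2 gives 90% (68.3–98.8); k = 5 gives 75% (50.9–91.3); k = 10 gives 50% (27.2–72.8).
- n = 30 (CAR T cohort): k = 3 gives 90% (73.5–97.9).
- n = 10 (Other Adult Solid Tumor cohort): k = 2 gives 80% (44.4–97.5).

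**4. Illustration of bias.** Assumptions: log10 baseline normal with SD 0.5–0.7; log10 rise normal with mean 1 (10-fold) and SD 0.3, independent of baseline; a share q of baselines above the ULOQ.

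- True 4-fold rate = Φ((1 − 0.602)/0.3) = 0.908.
- Share with baseline above ULOQ/4 = 1 − Φ(z − 0.602/SD), where z is the upper-q normal quantile.
- Reported 4-fold rate = 0.908 × (1 − that share), because every true responder at or below ULOQ/4 still shows the rise.
- Log10 reported GMFR = 1 − E[post excess over ULOQ] + E[baseline excess over ULOQ], both on the log10 scale.

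Example with SD 0.5 and q = 10%. The share is 1 − Φ(1.282 − 1.204) = 0.469, so the reported rate is 0.908 × 0.531 = 48%. The expected excesses are 0.455 (post) and 0.024 (baseline), so GMFR = 10^(1 − 0.455 + 0.024) = 10^0.569 = 3.7.

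| Baselines above ULOQ | Share above ULOQ/4 | Reported 4-fold rate (true 91%) | Reported GMFR (true 10) |
|---|---|---|---|
| 0.1% | 1–3% | 88–90% | 8.8–9.5 |
| 1% | 7–13% | 79–84% | 6.9–8.2 |
| 5% | 22–33% | 61–71% | 4.8–6.0 |
| 10% | 34–47% | 48–60% | 3.7–4.7 |

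In each range the end nearer the truth belongs to SD 0.7. Limiting the denominator to baselines at or below ULOQ/4 returns 91% in every row.

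**The case against.** **Scope of the cap.** The sentence follows one limited to GMT summaries and sits in the nAb paragraph. Its reach to individual fold rises, and to bAb, is an inference. This stands. It remains the natural reading, since the sentence carries no limit and no alternative is given, but the plan should say so.

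**Booster failure.** A reader might infer that a participant near the ceiling is counted as a booster failure. The documents define no such category. Under the cap that participant is a non-responder in the fold-rise percentages and under the third seroconversion criterion, but the second criterion could count the same person as seroconverted.

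**Frequency.** A reader might take the cap as a sign that the plan expects many values above the ULOQ. A rule for out-of-range values is not a forecast. Section 2.4.5 cites a 16% serologic response on BTK inhibitors, section 2.4.4 anticipates 40–60% seroconversion after CAR T therapy, and section 2.5.1 calls a third dose only moderately effective at raising titers. Many baselines in those cohorts may be low, where the ceiling is irrelevant. The illustration has no seronegative group and gives everyone the same mean rise, so it cannot serve as a forecast.

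**Use of the results.** There is no hypothesis test, the responder percentages are descriptive, and no analysis by booster number is specified. GMTs with median and maximum at each timepoint would partly reveal values at the ceiling. Section 7.3.2 provides backup samples for further testing, so some values might be resolved by repeat assay. These points limit the consequence, but none gives a rule for values above the ULOQ or shows how many participants could not meet a threshold.

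**Conclusion.** The point holds conditionally. If the cap reaches fold rises, a baseline above ULOQ/4 rules out an observed 4-fold rise by arithmetic alone, and GMFR moves toward 1. The size cannot be derived from the documents: it is nil for the 4-fold rule if no baseline exceeds ULOQ/4, and otherwise depends on the unknown ULOQ and baseline titers, with the table above as a range under stated assumptions.

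It is also tempting to conclude that less immunosuppressed cohorts, or third boosters, will look worse than others because of the assay. The ceiling could do this: with equal true 10-fold rises, baseline SD 0.6 and mean baselines 2 and 1 log10 below the ULOQ, the reported GMFRs are 9.6 and 5.6 and the 4-fold rates 90% and 68%. But nothing in the documents shows that baselines differ in this way. Separately, and whatever the ULOQ, the overlap between the second and third seroconversion criteria is a defect in the text. The change is worth making because it is cheap and uses data already collected.

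**What to change.** In section 11.4.2.1:

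- (a) State that the ULOQ rule applies to the fold-rise and seroconversion endpoints and to bAb, and use the actual value where one is available.
- (b) Report, by cohort and booster number, the count with baseline above ULOQ/4 and the count of post-vaccination values at the ULOQ.
- (c) Keep the all-participant percentages. Add supplementary 4-, 3- and 2-fold percentages limited to baselines at or below ULOQ/4, ULOQ/3 and ULOQ/2, and a seroconversion percentage limited to baselines at or below ULOQ/4.
- (d) Where any value exceeds the ULOQ, give a GMT and GMFR that treat it as right-censored (for example a censored-normal model on log titer) beside the capped estimate.
- (e) Limit the second seroconversion criterion to baselines from LOD to below LLOQ, and make the same change where the criteria appear in section 3.2.

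Cost: wording and modest programming, with no new samples or visits. The supplementary percentages have smaller denominators and wider intervals, and restricting on baseline changes the population differently in each cohort. The censored model may be unstable in cohorts of 10 to 30. If the counts in (b) are zero, (c) and (d) add nothing and can be dropped.

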11.4.2.2 Safety Analyses

Safety and reactogenicity will be assessed by clinical review of all relevant parameters including solicited ARs (local and systemic events), unsolicited AEs, SAEs, AEs leading to discontinuation, safety laboratory test results, vital signs, and physical examination findings.

Solicited ARs and unsolicited AEs will be coded by system organ class (SOC) and preferred term according to the MedDRA for adverse reaction terminology. The Toxicity Grading Scale for Healthy Adult and Adolescent Volunteers Enrolled in Preventative Vaccine Clinical Trials (DHHS 2007) is used in this study with modification for rash, solicited ARs, unsolicited AEs, and vital signs.

Rash will be graded as:

- Grade 0 = no rash
- Grade 1 = localized without associated symptoms
- Grade 2 = maculopapular rash covering $< 50\%$ body surface area
- Grade 3 = urticarial rash covering $> 50\%$ body surface area
- Grade 4 = generalized exfoliative, ulcerative or bullous dermatitis

All safety analyses will be based on the Safety Set, except summaries of solicited ARs which will be based on the Solicited Safety Set. All safety analyses will be provided overall and by cohort.

The number and percentage of participants with any solicited local AR, with any solicited systemic AR and with any solicited AR during the 7-day follow-up period after each injection will be provided with a 2-sided 95% exact CI using the Clopper-Pearson method.

Number and percentage of participants with unsolicited AEs, SAEs, Grade 3 or higher ARs and AEs, treatment-related AEs and SAEs, and AEs leading to discontinuation from study vaccine or participation in the study will be summarized. Unsolicited AEs will be summarized by system organ class and/or preferred term coded by MedDRA.

For treatment-emergent safety laboratory tests results, the raw values and change from baseline values will be summarized by timepoint.

The number and percentage of participants who have chemistry, hematology, coagulation, and vital signs results below or above the laboratory normal ranges will be tabulated by timepoint.

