7.1.3 Reactogenicity Assessments

Will include brief history for assessment of AE/SAEs just prior to and following vaccination, which includes an assessment of pain, tenderness, erythema, induration and warmth at the injection site; fever, chills, arthralgia/joint pain, malaise/fatigue, myalgia/body aches, headache, nausea, vomiting and abdominal pain.

The vaccination site will be examined at the end of the 15-minute observation period following each vaccination on Day 1 and Day 29 if applicable as well as all other timepoints if indicated.

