8.1.1 Adverse Events (AEs)

ICH E6 defines an AE as any untoward medical occurrence in a participant or clinical investigation Participant administered a pharmaceutical product regardless of its causal relationship to the study treatment. FDA defines an AE as any untoward medical occurrence associated with the use of a drug in humans, whether or not considered drug related.

An AE can therefore be any unfavorable and unintended sign (including an abnormal laboratory finding), symptom, or disease temporally associated with the use of medicinal (investigational) product. The occurrence of an AE may come to the attention of study personnel during study visits and interviews of a study recipient presenting for medical care, or upon review by a study monitor.

All AEs, including solicited local (injection site) and systemic (subjective and quantitative) reactions, will be captured on the appropriate data collection form and eCRF. Information to be collected for AEs includes event description, date of onset, assessment of severity, relationship to study product and alternate etiology (assessed only by those with the training and authority to make a diagnosis and listed on the Form FDA 1572 as an investigator), date of resolution, seriousness and outcome. AEs occurring during the trial collection and reporting period will be documented appropriately regardless of relationship. AEs will be followed through resolution.

Any medical condition that is present at the time that the Participant is screened will be considered as baseline and not reported as an AE. However, if the severity of any pre-existing medical condition increases, it should be recorded as an AE.

If an event meets both the criteria of a study endpoint and an adverse event, the event will be reported either as a study endpoint or as an adverse event (not both).

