8.1.1.1 Adverse Events Grading

All AEs (laboratory and clinical symptoms) will be graded for severity and assessed for relationship to study product (see definitions). AEs characterized as intermittent require documentation of onset and duration of each episode. The start and stop date of each reported AE will be recorded on the appropriate data collection form and eCRF. Changes in the severity of an AE will be documented to allow an assessment of the duration of the event at each level of intensity.

8.1.1.1.1 Severity of Event:

The severity of unsolicited AEs will be assessed by the investigator using the NCI Common Terminology Criteria for Adverse Events (NCI-CTCAE) version 5.0.

The severity of solicited AEs will be assessed by the investigator using the clinical abnormalities section of the FDA "[Toxicity Grading Scale for Healthy Adult and Adolescent Volunteers Enrolled in Preventive Vaccine Clinical Trials](#)".

The following grading system utilized for the events not listed in the above scales:

- * Mild (Grade 1): Events that are usually transient and may require only minimal or no treatment or therapeutic intervention and generally do not interfere with the Participant's usual activities of daily living.
 - Transient: Duration less than 48 hours

- Therapeutic Intervention: An action to alleviate the adverse event that does not require a medication or medical procedure, such as a change in diet, or application of cool pack or warm compress, or rest
- * Moderate (Grade 2): Events that are usually alleviated with additional specific therapeutic intervention. The event interferes with usual activities of daily living, causing discomfort but poses no significant or permanent risk of harm to the research participant.
- Therapeutic Intervention: Use of non-narcotic pain reliever or over-the-counter medication
- * Severe (Grade 3): Events interrupt usual activities of daily living, or significantly affects clinical status, or may require intensive therapeutic intervention. Severe events are usually incapacitating.
- Activities of Daily Living (ADLs): Negative impact on ADLs, such as missed work, unable to do housework or exercise
- Significantly Affects Clinical Status: A medically attended event – clinical care was sought from a healthcare professional
- Intensive Therapeutic Intervention: Required prescription medication, or intravenous fluids or medical procedure

8.1.1.2 Relationship to Study Product:

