8.1.2 Reactogenicity (Solicited AE)

Reactogenicity events are AEs that are common and known to occur following administration of this type of study vaccine. Study clinicians will follow and collect resolution information for any reactogenicity symptoms that are not resolved within 7 days.

Solicited AEs (i.e., reactogenicity) will be collected using memory aids and recorded on the appropriate source document from the time of each vaccination through 7 days post each vaccination (Days 1-8 for the first vaccination, and Days 29-36 for the second vaccination if applicable).

For this study, solicited AEs will be:

- Injection site Pain
- Injection site Erythema
- Injection site Edema/Induration
- Headache
- Diarrhea
- Fatigue
- Myalgia
- Arthralgia
- Nausea
- Fever
- Chills

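### The baseline for solicited reactions is set at screening, not just before each injection, so cancer-therapy symptoms that begin in between can be counted as systemic reactogenicity.

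*Combined protocol and SAP*

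**What the plan says.** Solicited local and systemic reactions through 7 days after each injection are the first primary safety endpoint listed in section 3.2. Section 11.4.2.2 summarises participants "with any solicited systemic AR and with any solicited AR during the 7-day follow-up period after each injection", with exact 95% intervals, overall and by cohort. It states no minimum grade, comparison with a pre-dose level or restriction to related events. Appendix D grades on an absolute scale: fatigue, myalgia or headache that does not limit activity is already Grade 1.

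The protocol does contain a baseline rule. Section 8.1.1 provides: "Any medical condition that is present at the time that the Participant is screened will be considered as baseline and not reported as an AE". It adds that "if the severity of any pre-existing medical condition increases, it should be recorded as an AE". The rule applies to solicited events, since the same section says "All AEs, including solicited local (injection site) and systemic (subjective and quantitative) reactions, will be captured", and section 8.1.2 says "Reactogenicity events are AEs that are common and known to occur following administration of this type of study vaccine".

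Section 7.1.3 calls for a "brief history for assessment of AE/SAEs just prior to and following vaccination". Neither section 8.1.1 nor section 11.4.2.2 refers to that reading.

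**The concern.** The population makes the reference point important. Table 3 places intensive leukemia, lymphoma and myeloma regimens in Cohort 3 and lighter active therapy in Cohort 2. Section 5.2.2 excludes people who are acutely ill or febrile around screening, but no criterion excludes treatment-related fatigue, nausea, headache or myalgia. A treatment cycle that begins between screening and an injection can produce the symptoms that the plan solicits.

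Every participant is vaccinated, so the trial has no internal background rate to set against the result. The percentages are reported by cohort, and the hematologic vaccine-naïve cohorts are defined by intensity of immunosuppression. Any contamination could therefore differ between them. Section 8.1 also wants adverse events to be comparable with the Phase 3 trial, which section 2.5.2 describes as having a placebo group. Elsewhere the plan does use a baseline: laboratory values are summarised as change from baseline, and antibody titers as fold rise over Day 1.

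**Working it through.** The plan gives no event rate or precision target for this endpoint, so it has no figure to reproduce. The check has three steps.

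**1. What the 8.1.1 rule removes**

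| Course of a systemic symptom | Under 8.1.1 | Counted in 11.4.2.2? |
|---|---|---|
| Present at screening, never worse | Baseline, not an AE | No, if the rule is applied |
| Present at screening, worse before dosing, unchanged after | Worse than at screening | Can be |
| Absent at screening, present before dosing, no worse after | Not covered | Can be |
| Absent before dosing, starts within 7 days | New event | Yes |

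The second and third rows are the gap: nothing changed after the injection, yet no text removes the event.

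**2. Age of the reference**

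- Dose 1: screening may be up to 28 days earlier (section 4.8.3), or on the same day (section 6.1.2.1).
- Dose 2 (Day 29): 28 days after dose 1, so up to 28 + 28 = 56 days after screening on the nominal schedule.
- First booster for a vaccine-naïve participant: at least 4 weeks after dose 2 (section 3.1), so at least 28 + 28 = 56 days after dose 1.
- Later boosters: at least 28 days more each.

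Section 6.1.3 restarts the visit calendar at each booster but does not say that the symptom baseline restarts. Appendix C sets baseline before consent for leukemia, but gives way to the protocol text where the two differ.

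**3. Possible size**

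All inputs here are assumptions; the documents supply none.

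- Share with a Grade 1 or higher solicited symptom on the dosing day: 10%, 20% or 30%.
- Share of these who still report it in the 7 days: 90%.
- Share not already present at screening, and so not removed by 8.1.1: all or half.
- True rate of vaccine reactions, p: 50% or 70%, independent of background.

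Unremoved background is q = prevalence × 0.9 × share not removed. The observed rate is 1 − (1 − p)(1 − q), so the excess over p is q(1 − p).

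| Prevalence | Share not removed | q | Excess, p = 50% | Excess, p = 70% |
|---|---|---|---|---|
| 10% | half | 4.5% | 2.25 points | 1.35 points |
| 10% | all | 9% | 4.5 | 2.7 |
| 20% | half | 9% | 4.5 | 2.7 |
| 20% | all | 18% | 9 | 5.4 |
| 30% | half | 13.5% | 6.75 | 4.05 |
| 30% | all | 27% | 13.5 | 8.1 |

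The range is 1.35 to 13.5 points. In a cohort of 20 that is 20 × 0.0135 = 0.27 to 20 × 0.135 = 2.7 extra participants counted. For comparison, the exact 95% interval is 27.2% to 72.8% for 10 of 20, and 38.6% to 61.4% for 40 of 80.

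**The case against.** A reader might infer that any Grade 1 symptom after an injection counts whatever came before it, so that all therapy symptoms present on the dosing day become reactogenicity. The documents do not support that. Section 8.1.1 excludes a symptom present at screening and no worse, in a section that names solicited reactions. That part of the objection stands and limits the point to symptoms that arise or worsen after screening.

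Other safeguards exist. Screening can fall on the dosing day, and history is reviewed again at Day 1 and Day 29. Section 7.1.4 says memory aids are not source documents, so staff interview the participant and complete the source themselves. Section 8.1.1.1 says "All AEs (laboratory and clinical symptoms) will be graded for severity and assessed for relationship to study product", and alternate etiology is collected. Grade 3 or higher events and treatment-related AEs are summarised separately. These may reduce miscounting in practice, but none is stated to reset the baseline or to filter the solicited table.

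The size is assumed, and within one 20-person cohort it is smaller than the sampling uncertainty. That is fair, but sampling error shrinks as cohorts are pooled and this bias does not. The study tests no hypothesis (section 11.1), so no formal comparison fails. A claim that a difference between cohorts would be wholly due to treatment symptoms would be speculation.

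Finally, an increase-based rate has a bias of its own: it drops true reactions that do not exceed an existing grade. That is a good reason not to let it replace the planned figure.

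**Conclusion.** The concern holds in a limited form. Therapy symptoms that begin or worsen between screening and an injection, and are present at dosing, can be counted as systemic reactogenicity in a primary safety endpoint. The plan collects a pre-dose history that could identify most of them but does not use it. Local reactions and Grade 3 or higher summaries should be little affected.

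The documents do not fix the size. The range of roughly 1 to 14 points rests on the assumed prevalence, persistence, share removed by 8.1.1, true reaction rate and independence. The background shares of 4.5% to 27% should not themselves be read as the overstatement. They would be the observed rates only if the vaccine caused no systemic reactions. Participants with both a background symptom and a true reaction are counted once, which shrinks the excess by the factor 1 − p.

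**What to change.** - On the dosing-day form, record a grade for every solicited systemic item before each injection, boosters included. Add diarrhea, which section 8.1.2 solicits but section 7.1.3 does not ask about. Chills and arthralgia have no row of their own in Appendix D, so state which scale applies and use it both before and after the injection.
- In section 8.1.1 or 8.1.2, state that this pre-vaccination grade is the baseline reference for solicited reactions.
- In section 11.4.2.2, report the percentage whose worst grade in the 7 days exceeds the pre-dose grade, overall and by cohort, with its exact interval, alongside the planned any-reaction percentage.

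The cost is one form field per item at each injection and one more table. Most of the history is already taken, and clinical management does not change. The increase-based figure misses true reactions no worse than an existing symptom, and it still counts therapy symptoms that first appear after the injection. The two figures should be shown and read together. For injections given before the form changes, the pre-dose grade may not be recoverable; report how many participants lack it.
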